3. Transplant rejection suspected by unexplainable increase in liver enzymes *and* proven by liver biopsy will be considered as a Grade 3 AE that requires medical intervention (MAAE). Each patient with rejection will be withdrawn from further vaccination if the rejection is considered to be possibly or definitely related to the vaccine. Such patients will be followed until the end of the study (week 60) so that additional safety data may be collected. Additional immunogenicity data may be obtained if the patient had received at least two doses of vaccine before allograft rejection became apparent and if seroprotective levels were evident when last tested.

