7.4 Clinical Hold on Further Group Enrollment

- 1. If at any time a Grade 3 AE or SAE develops that is considered to be definitely related to vaccination, then an immediate hold on further enrollment will be placed on the group the patient belongs to. Also, neither the affected individual nor other participants in that group will be given further vaccine inoculations. This applies to all groups.
- 2. If transplant rejection develops that is considered to be definitely related to vaccination, this will be considered as an SAE that is medically attended (MAAE) and a clinical hold on further enrollment will be enacted for the group (C) the patient belongs to. In addition, no further vaccination will be given to the affected individual.
- 3. Should 2 patients in any group have a grade 3 AE or SAE considered to be *possibly* related to vaccine, then an immediate hold on both further enrollment and repeat inoculations in that group will be enacted.

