7.5. Subject Withdrawal

- 1. Patients with a Grade 4 adverse event that is possibly or definitely related will immediately be withdrawn from the study and followed clinically until resolution of the event occurs. Every effort will be made to have the patient continue with the study visits to collect additional safety data up to 52 weeks after the last dose of vaccine.
- 2. Patients will be withdrawn from the study if (a) it is the opinion of the investigator that further dosing or follow up should be withheld because of poor study compliance or (b) if the patient

wishes to end participation. Patients who are excluded from further vaccine for reasons of safety will continue to meet study visit requirements to obtain additional safety data.

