10.6 Definitions

An adverse event will be considered as "unexpected" if not included in the Investigator's Drug Brochure (Feb, 2019) or not listed at the specificity or severity observed in the study (Code of Federal Regulations Title 21, April 1, 2018). Definitions of grade severity of adverse events will be considered as follows:

Grade 1: mild, asymptomatic or mild symptoms; clinical or diagnostic observations only; intervention not needed.

Grade 2: Moderate; minimal local or noninvasive intervention indicated.

Grade 3: Severe or medically significant but not immediately life threatening;

hospitalization or prolongation of hospitalization indicated; disabling; limiting self care

Grade 4: Life threatening; urgent intervention needed

Grade 5: Death related to AE.

Adverse event: any untoward medical occurrence associated with the use of the vaccine

Serious adverse event: resulting in any of the following: death, potentially life-threatening, resulting in hospitalization, prolongation of hospitalization, persistent incapacity, substantial disruption of the ability to conduct normal life functions, or a congenital anomaly.

Medically attended adverse event (MAAE): any adverse event that leads to an evaluation by a healthcare professional.

Potentially immune mediated medical conditions (pIMMC): A list of these provided by the FDA is included in Appendix 4.

Grading of AEs will be according to Common Terminology Criteria for Adverse Events (CTCAE) Version 5.0, November 27, 2017 by the U.S. Department of Health and Human Services/National Institute of Health/National Cancer Institute.

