11.4. Termination Criteria

Termination of the study requires an assessment of the grade and number of SAEs, as well as their relatedness to the drug. A three point scale will be used for relatedness: unrelated, possibly related, and definitely related. Both sets of parameters are defined in Section 7.3, page 18. Definitely related will be assessed both temporally in relation to vaccine administration and will require the absence of other possible explaining factor(s).

- 1. The study will be terminated if a Grade 4 AE or death occurs that is considered possibly or definitely related to vaccine.
- 2. As previously mentioned in Section 7.4, page 19, a hold will be placed on further enrollment into a group if a patient develops a Grade 3 or SAE that is considered to be definitely related to vaccine. If this occurs, the study will be terminated if a second patient in a different group subsequently develops a grade 3 AE or SAE that is considered to be definitely related. All patients will continue to be followed for at least 52 weeks after the last dose of vaccine to collect additional safety data.
- 3. In the absence of a previous clinical hold on enrollment in any group, the study will be terminated if at any time *two patients*, *one each from different groups*, *concurrently develop* a Grade 3 AE or SAE both of which are considered definitely related. Such patients will continue to be followed for at least 52 weeks after the last dose of vaccine to collect additional safety data.

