Abdominal Pain	None	On a scale 1-10 (with 10 being the worst) 1 2 3 4 5 6 7 8 9 10	On a scale 1-10 (with 10 being the worst) 1 2 3 4 5 6 7 8 9 10	On a scale 1-10 (with 10 being the worst) 1 2 3 4 5 6 7 8 9 10	
Systemic					
Fever	YES/NO	99-101 F	> 101 to 103 F	> 103	
Fatigue	YES/NO	Minimal	Moderate	Severe	
Overall assessment*	No change	Feel slightly worse	Feel moderately worse	Feel much worse	
Social Function					
	Normal	Occasional limitation	Several times weekly	Absence from work	Home ridden
Food tolerability	No problem	Minimally affected	Moderately affected	Severely affected	

Comments	 	 	

Appendix 3. Quick View Table of Criteria for Subject Withdrawal, Vaccine Withdrawal, and Study Termination

Adverse Event	Relatedness	Subject	Vaccine	Anticipated Follow up	Study Termination
	Not Poss Def	withdrawal	Withdrawal		
Death	Not	-	-	-	No*
	Possibly	-	-	-	Yes
	Definitely	-	-	-	Yes
Grade 4	No	No	No	Until 52 weeks after last vaccine dose	No*
	Possibly	Yes	Yes	Until 52 weeks after last vaccine dose	Yes
	Definitely	Yes	Yes	Until 52 weeks after last vaccine dose	Yes
Worsened underlying	Regardless of	Yes	Yes	Until 52 weeks after last vaccine dose	No, but hold on further enrollment & vac-
disease in Group A patient	relatedness				cine in group A if AE is definitely related**
	Not	No	No	Until 52 weeks after last vaccine dose	No
	Possibly	No***	Yes	Until 52 weeks after last vaccine dose	No
Grade 3 AE or SAE in any	Definitely	No***	Yes	Until 52 weeks after last vaccine dose	Yes, if a second patient in different group
patient group					has a Grade 3 AE or SAE that is also
					definitely related to vaccine $^{\Omega}$ If this does
					not occur, a hold on further enrollment &
					vaccine in the group the patient belongs to
Liver allograft rejection	Possibly	No***	Yes	Until 52 weeks after last vaccine dose	No
	Definitely	No***	Yes	Until 52 weeks after last vaccine dose	Yes, if a second patient in different group
					has a Grade 3 AE or SAE that is also
					definitely related to vaccine $^{\Omega}$ If this does
					not occur, a hold on further enrollment &
					vaccine in group C will be enacted.

^{*}The finding of a death or Grade 4 AE that is considered unrelated to vaccine will not be considered sufficient to terminate the study nor place a hold on further enrollment in that group.

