^{**}The finding of a Grade 3 AE or SAE that is considered definitely related to vaccine will place a hold on further enrollment in Group A and all other groups (B and C). Should two subjects in one group have the same or similar Grade 3 AE or SAE assessed as *possibly* related, then enrollment and vaccination in that group will also be put on hold.

^{***} If patient meets criteria for vaccine withdrawal they will still be followed for safety until week 60.

 $^{^{\}Omega}$ Study termination will occur if two patients, one each from two different groups, develop a Grade 3 AE or SAE considered to be definitely related to vaccine.

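### Section 7.3(3) fixes enzyme-suspected, biopsy-proven liver rejection at Grade 3 without saying 'at least', so a non-fatal but life-threatening rejection conflicts with the single-event termination rule in 11.4(1)

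*Protocol*

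**What the plan says.** All references are to the Protocol.

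- **7.3, opening and item 3.** The section opens by adopting CTCAE version 5.0 grading for withdrawal decisions. Item 3 then deals with rejection that is both suspected from an unexplained enzyme increase and proven by biopsy. Such an event "will be considered as a Grade 3 AE that requires medical intervention (MAAE". Dosing of that patient stops if the rejection is possibly or definitely related.
- **10.6, severity scale.** "Grade 3: Severe or medically significant but not immediately life threatening"; then "Grade 4: Life threatening; urgent intervention needed".
- **11.4, item 1.** "The study will be terminated if a Grade 4 AE or death occurs that is considered possibly or definitely related to vaccine". The opening paragraph of 11.4 refers back to 7.3 for the definitions of grade and relatedness.
- **7.5, item 1.** "Patients with a Grade 4 adverse event that is possibly or definitely related will immediately be withdrawn from the study".
- **7.4, items 1 and 2.** A definitely related Grade 3 AE or SAE stops enrollment and dosing in that patient's group. A definitely related rejection is classed as an SAE, with an enrollment hold on Group C and no more vaccine for the affected patient.
- **7.4, item 3.** If two patients in one group each have a possibly related Grade 3 AE or SAE, "then an immediate hold on both further enrollment and repeat inoculations in that group will be enacted".
- **Appendix 3.** The Grade 4 row says yes to termination for possibly and for definitely related events. The liver rejection row is split by relatedness only. It says no to termination if possibly related. If definitely related, it says yes only when a second patient in a different group also has a definitely related Grade 3 AE or SAE; otherwise a hold on enrollment and "vaccine in group C will be enacted".

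**The concern.** The grade given to a related event decides which stopping rule applies. Everywhere else the grade follows severity; for rejection it is set in advance. That does no harm while the rejection is in fact severe but not life-threatening. When it is life-threatening, the preset grade contradicts the protocol's own definition of Grade 3, and the event could be kept out of the one rule that stops the trial after a single event.

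Safety is a co-primary objective (5.0), and rejection is the graft-specific harm for which the protocol wrote its own clauses. If the grade is left open, the choice between stopping and continuing would be made after the event, by people who know what happened. A stopping rule set in advance is meant to avoid that.

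**Working it through.** No stated figure needs to be reproduced. The check follows one event through the rules: a rejection that meets both conditions of 7.3(3), is life-threatening but not fatal, and is judged possibly or definitely related.

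**Step 1. Grade.** By severity under 10.6 and CTCAE the event is Grade 4, because the definition of Grade 3 excludes it. By 7.3(3) it is Grade 3. The two cannot both hold.

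**Step 2. Outcome under each grade.**

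| | Graded 4 by severity (7.5(1), 11.4(1), Appendix 3 Grade 4 row) | Graded 3 by 7.3(3) (7.4, 11.4(2)–(3), Appendix 3 rejection row) |
|---|---|---|
| Possibly related: study termination | Yes, after 1 event | No |
| Possibly related: automatic hold | Not needed | Group C hold under 7.4(3), only after a second Group C patient has a possibly related Grade 3 AE or SAE |
| Definitely related: study termination | Yes, after 1 event | Only with a second definitely related Grade 3 AE or SAE in a different group (2 events in all) |
| Definitely related: hold after the first event | Not needed | Group C hold (7.4(1), 7.4(2), rejection row) |
| Further dosing of the affected patient | Stops | Stops |
| Formal subject withdrawal | Yes | No |
| Safety follow-up of the affected patient | Sought to 52 weeks after last dose | Continues (week 60 in 7.3(3); 52 weeks after last dose in Appendix 3) |

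The termination outcome differs at both levels of relatedness. The affected patient's dosing does not differ, and the difference in formal withdrawal is mostly nominal because safety follow-up is sought either way.

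**Step 3. Does any text settle priority?** None was found. 11.4(1) has no exception for rejection, which favors Grade 4. But 11.4 takes its grading from 7.3, the section that fixes rejection at Grade 3, and 7.4(2) has no branch for a Grade 4 rejection. Those two points favor Grade 3. Appendix 3 does not rank its rows.

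**Step 4. Extent of the hold in the definitely related case.** The double-asterisk footnote to Appendix 3 says that a definitely related Grade 3 AE or SAE "will place a hold on further enrollment in Group A and all other groups (B and C", which is wider than the one-group hold in 7.4(1), 7.4(2) and the rejection row. This affects how far a hold reaches, not whether the study terminates.

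**Step 5. How often could it arise?** Group C has 6 of the 18 planned patients. 7.2 excludes allografts less than three years old and rejection within the past year, and 4.3 calls the rejection risk minimal. The documents give no rate from which a probability could be computed.

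**The case against.** The strongest reply is that Grade 3 in 7.3(3) is a floor. The item concerns vaccine withdrawal, begins from an enzyme rise, and makes sure that such a rejection is never graded too low. It says nothing about ending the study. CTCAE grading is adopted in 7.3 and again in 10.6, and 11.4(1) applies to any related Grade 4 event. A life-threatening complication of the rejection could also be recorded and graded as an event of its own on the Appendix 1 form, and so reach 11.4(1) by another route. This reading is plausible and probably intended. It is not written, however, and the separate-event route depends on how the investigator chooses to record the episode.

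Several stronger readings are tempting, and the documents do not support them:

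- **That every biopsy-proven rejection is misgraded.** 7.3(3) requires an unexplained enzyme rise as well as biopsy proof, and Grade 3 may be right for a rejection that is not life-threatening.
- **That a fatal rejection could escape the stopping rule.** A related death terminates the study under 11.4(1) by its own words.
- **That 7.4(3) is the only safeguard after a possibly related rejection.** It is the only automatic brake. The investigator can also withhold dosing under 6.7(3), the investigator reviews safety data weekly (15.0), and Grade 3 and Grade 4 events go to the IRB and sponsor on the same timetable (10.5).
- **That a large number of patients would go on being vaccinated.** The count could be anything from 0, if all others have finished dosing, to 18 − 1 = 17, if none has and no one uses discretion. A range that wide says little about the likely harm.

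**Conclusion.** The conflict is real and narrow. For a non-fatal, life-threatening rejection that meets 7.3(3) and is judged possibly or definitely related, the protocol supports two different answers to whether the study stops, and it does not choose between them. Read literally, 7.3(3) lets the event bypass the single-event rule: the number of events needed to end the study goes from 1 to 2 in different groups if definitely related, and to no termination at all if possibly related.

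The severity is low. The case is confined to six patients selected to be at low risk of rejection, the affected patient's dosing stops either way, discretionary checks remain, and the sensible reading would apply 11.4(1). The point concerns safety rules only and does not touch the immunogenicity endpoints or their analysis. The conclusion assumes only that a rejection can be life-threatening without being fatal.

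**What to change.** Make three short edits:

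1. In 7.3(3), say that such a rejection is *at least Grade 3, graded higher by CTCAE if life-threatening or fatal*.
2. In Appendix 3, relabel the rejection row as Grade 3 rejection, so that a Grade 4 rejection is read from the Grade 4 row and a fatal one from the death row.
3. In 7.4(2), add that a Grade 4 rejection possibly or definitely related to vaccine follows 7.5(1) and 11.4(1).

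The cost is one clause, one row label and one sentence in a wording amendment. No new data, visits or patients are needed, and handling of rejection that is not life-threatening does not change.

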7.4 Clinical Hold on Further Group Enrollment

- 1. If at any time a Grade 3 AE or SAE develops that is considered to be definitely related to vaccination, then an immediate hold on further enrollment will be placed on the group the patient belongs to. Also, neither the affected individual nor other participants in that group will be given further vaccine inoculations. This applies to all groups.
- 2. If transplant rejection develops that is considered to be definitely related to vaccination, this will be considered as an SAE that is medically attended (MAAE) and a clinical hold on further enrollment will be enacted for the group (C) the patient belongs to. In addition, no further vaccination will be given to the affected individual.
- 3. Should 2 patients in any group have a grade 3 AE or SAE considered to be *possibly* related to vaccine, then an immediate hold on both further enrollment and repeat inoculations in that group will be enacted.

7.5. Subject Withdrawal

- 1. Patients with a Grade 4 adverse event that is possibly or definitely related will immediately be withdrawn from the study and followed clinically until resolution of the event occurs. Every effort will be made to have the patient continue with the study visits to collect additional safety data up to 52 weeks after the last dose of vaccine.
- 2. Patients will be withdrawn from the study if (a) it is the opinion of the investigator that further dosing or follow up should be withheld because of poor study compliance or (b) if the patient

wishes to end participation. Patients who are excluded from further vaccine for reasons of safety will continue to meet study visit requirements to obtain additional safety data.

8.0. TREATMENT OF SUBJECTS

Patients will be given 0.5 ml of Heplisav-B in the clinic office on the 8th floor of the Sammons Cancer Center by skilled nursing staff. It will be delivered by IM injection in the deltoid region.

8.1. Medication

The patient will continue to take all prescription drugs and may be on prophylactic nucleoside analogue therapy for HBV infection.

8.2 Timing of Vaccine Initiation in Relation to Time of Initiation of Immune Suppressive Medication.

Patients in Group A will be taking ISDT when seen at the screening visit. They must have stable underlying disease to be eligible for the study. Provided they are eligible, the first vaccine inoculation will be 4 weeks after screening. Patients with malignancy (Group B) will either be given vaccination prior to chemotherapy (depending on the planned schedule for initiation of chemotherapy) or alternatively as shortly as possible after chemotherapy has already begun. Patients who have been transplanted (Group C) will be receiving ISDT at the time they are first seen. Those transplanted for hepatitis B will have been taking ISDT for three or more years when first vaccinated. The same post-transplant interval will also apply to recipients of anti-HBc positive organs.

8.3 Monitoring for Subject Compliance

Patients will be called 24-48 hours before each visit to remind them. A failure to appear will result in a call back by the principal investigator's coordinator during work hours or at times by the principal investigator after work hours. The patient will be offered a suitable time for reappearance within 3 to 5 working days of the initially scheduled visit. This has proven to be successful in the investigator's previous clinical research studies. At each visit, the principal investigator will provide continuous education about the importance of continued participation to minimize noncompliance.

9.0 ASSESSMENT OF EFFICACY

9.1 Efficacy Parameters

- Assessment of proportion of subjects with anti-HBs titers ≥ 10 mIU/ml at each study interval.
- Assessment of percentage of subjects with anti-HBs titers ≥ 100 mIU/ml at each study interval.

- Assessment of geometric mean titers for all subjects at each study interval.
- Assessment of reasonable safety in patients who are medically immunosuppressed

9.2 Method and Timing

Assessment of efficacy will require quantitative anti-HBs assessments at each of the visits that are specified in Table 1. This includes week 4,8,12, 24 and 60 week visits.

10. 0. ASSESSMENT OF SAFETY

10.1 Safety Endpoints

Patient safety is a co-primary objective of the study and the following endpoints will be considered and used for future reporting:

- 1. Proportion of subjects with unsolicited AEs after inoculation. All adverse events including those that are unsolicited will be recorded for a period of 28 days after vaccine administration, and at each visit changes in the patient's state of health will be recorded on the Appendix 1 (AE capture form) and as needed on the Appendix 2 form. To facilitate accurate reporting in real time, patients will be questioned at a weekly telephone assessment and seen by the principal investigator should this appear warranted. Photographic evidence by the patient may be requested between visits for certain AEs.
- 2. Proportion of subjects with SAEs. The study will capture all SAEs (and Grade 3 AEs) that occur through one year after the last dose of vaccine. To facilitate accurate reporting, all patients with these events will be seen within 48 to 72 hours and acted upon if needed. Follow up will continue until at least 52 weeks after the last dose of vaccination Data will be collected on the Appendix 1 safety form and in the case of Group A, Appendix 2 as well.
- 3. Proportion of subjects with MAAEs. All MAAEs that occur within one year of the last vaccine dose will be captured. Patients will be handled as in 2 Above.
- 4. Proportion of subjects with pIMMCs. This will be captured for a period of 52 weeks after the last dose of vaccine. Patients will be handled as in 2 and 3 above. Data will be reported on both the Appendix 1 and Appendix 2 safety forms.
- 5. Proportion needing an increase in immune suppressive medication. All concomitant medications used during the 28 day period following vaccination and those used to treat MMAEs or SAEs during a 12 month period after the last dose of vaccine will be recorded. Special attention will be given to new or dose adjusted immune suppressive medications that are needed to treat adverse events. Data will be captured in Appendix 1 (adverse event capture form) under the header "Type Intervention."

10.2 Further Safety Considerations:

- a. C-reactive protein blood testing will be used to assess augmentation of inflammatory disease activity in Group A.
- b. Clinical assessment by principal investigator at each study visit. A focused physical exam will be part of the safety data base. Photographic evidence of underlying disorder in Group A patients may be obtained as needed for documentation.
- c. After vaccine administration, patients will be monitored for any immediate or unusual injection site reactions. After leaving the clinic, reactions and AEs will be delineated by weekly post inoculation telephone assessment at which point photographic evidence of an underlying dermatologic disorder may be requested if deemed necessary.
- **10.3 Pregnancy Assessments.** Potentially child bearing females will have a serum pregnancy test at the screening visit. If positive, they will be ineligible for the study. A urine pregnancy test will be taken prior to vaccination at the visits in which vaccine administration is anticipated, including the visit for the week 12 dose. Vaccine will be withheld if the test is positive at any time. A urine pregnancy test will also be repeated at week 24. Patients who are found to be pregnant after one or more doses have been given will be asked to continue with the per protocol visit schedule until week 60 so that additional safety data on pregnancy outcome can be collected

10.4 Method and Timing.

Each patient will be asked to report adverse events at the time of weekly telephone assessments or as needed after each dose of vaccine. At each study visit, all relevant safety data will be captured and kept in a patient binder. Data will be collected at each visit in regard to safety outcomes (AE Capture Form, Appendix 1, and Patient Related Outcome Assessment form, Appendix 2).

